We plan to conduct an open-label, single-center, single-arm three-period study. We aim to recruit 25 adolescents aged 13-18 years with poorly controlled T1D as evidenced by Hemoglobin A1c \geq 12% or a 30% annual risk of developing DKA in the following year according to a predictive model developed at our institution. At a threshold value of probability of admission \geq 0.3 (95% specificity) our model can identify a high-risk subset of approximately 8% of the patients who collectively have a 40% probability of admission in the 12 months following assessment.⁸ We will obtain a written informed consent from guardians and assent from study participants before any study-related activities. We will obtain each patient's demographic information, time since diagnosis, previous hospital admissions. Patient Health Questionnaire (PHQ-9A)⁹ and a point-of-care hemoglobin A1c as standard of care. We will administer a quality of life questionnaire (assessed by the Pediatric Quality Life Inventory for teens 13-18, PedsQL4.0)¹⁰, a self-efficacy and self-management questionnaire (assessed by The Self-Efficacy for Diabetes Self-Management measure (SEDM)¹⁰), and a questionnaire to assess parent-child collaboration in diabetes care (assessed by the Collaborative Parent Involvement Scale¹²).

The first phase of the study will be a surveillance phase in which a blinded Dexcom G6 will be used to obtain baseline values including time in range, percent highs, and percent lows, and percent CGM use. We will use this phase as a run-in period to reduce the chance of noncompliance with the study.

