Participants who wore the device at least 60% of the time will then proceed to the second phase of the study which aims to provide a nonblinded CGM for patient use with professional real-time monitoring. If the CGM is worn less than 60% of the time, the participant may be withdrawn from the study at the discretion of the study investigator. Participants will be encouraged to use CGM data for insulin dosing and to monitor their own blood glucose levels. Additionally, participants will share their CGM data with our clinic and with their legal guardians, utilizing the real-time share/follow Dexcom function. Clinical personnel, who could be either endocrinology fellows, endocrinology nurse practitioners or certified diabetes educators, will provide direct supervision and will communicate routinely with participants and guardians using secure text messaging (see Procedure section for more details). Remote monitoring will occur on 7 days per week between 8:00 AM and 8:00 PM. Clinical personnel will have real-time access to patient blood glucose data and will make management recommendations based on the diabetes management plan, will review insulin trends every week, will provide motivational texts to participants, and will respond to any diabetes-related concerns raised by participants. Participants

will receive \$10 gift card for every study follow-up visit completed, with a total compensation of \$30 per participant.

The third study phase will provide unblinded CGM to patients without real-time monitoring. Participants and their families will still have the ability to communicate with our clinic through routine clinically available means, mainly through the electronic patient portal and/or calling the urgent line. This study phase will be exploratory to assess whether any improvement in diabetes control after real-time monitoring continue to exist after real-time monitoring is withdrawn.

Inclusion criteria

- Age between 13-18
- Diagnosis of type 1 diabetes for at least six months.
- Both sexes and all ethnicities included.
- Subject and at least one parent able to communicate in English.
- Poorly controlled T1D as evidenced by a $\geq 30\%$ annual risk of developing DKA in the following year OR Hemoglobin A1c $\geq 12\%$
- Treated with subcutaneous insulin, either with a basal/bolus insulin regimen or a continuous subcutaneous insulin infusion (CSII) device.

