Schedule of procedures

Screening, Visit 1

Screening visit. It will include review of inclusion and exclusion criteria and obtaining informed consent from legal guardians and assent from participants. The visit is expected to take around one hour. The visit can be combined with Visit 2.

Participants will be recruited from either an endocrinology inpatient floor or the outpatient clinic.

Baseline, Visit 2

The visit will include review of diabetes history including current doses, prior hospitalizations, previous complications, and detailed medical and social histories and a complete physical examination that will include measurement of height and weight. A capillary blood sample will be obtained for HbA1c determination using the Alere Afinion device. A HbA1c from within two weeks of Visit 2 may also be used. A urine pregnancy test will be performed on females capable of becoming pregnant.

Participants and guardians will be introduced to the concept of a continuous glucose monitor in general, with specific details about how to apply, use, and share the Dexcom G6 data. Mandatory alarms will be set for participants and followers for blood glucose below 70 mg/dL, blood glucoses above 250 mg/dL, “urgent low soon”, “signal loss”, and “no reading” alerts. Participants may set extra alarms to personalize their diabetes alerts. Participants will also be taught to log their food and insulin intake into the CGM device.

Participants will complete the PHQ-9A, PEDS-QoL4, Self-Efficacy for Diabetes Self-Management measure (SEDM) questionnaire, and Collaborative Parent Involvement Scale. A blinded CGM will be placed on the participant with the goal to obtain baseline data for 10 days. A test secure text message will be sent through TigerConnect to guardian and participant, and they will be introduced to the messaging platform used. We will determine with the participants and parents their preferred contact hours and school hours to allow texting for non-urgent matters to be done at convenient times. This visit will take up to 2 hours.

Between Visit 2 and Visit 2T, participants and clinical staff will be notified if there is signal loss from the blinded CGM. Dexcom, Inc. will provide troubleshooting of the blinded CGM if any technical issues arise. Participants will be asked to continue taking care of their diabetes as usual and will not have access to the CGM data.

Telephone or Clinic Follow-up, Visit 2B or 2T

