This will be a telephone call scheduled 10 days (+ 4 days) by a clinical research staff member to review blinded CGM data for the purpose of logging CGM parameters including average glucose with standard deviation, time in range, percent highs, percent lows, and severe lows, and days with CGM data. If the CGM is worn less than 60% of the time, the participant may be withdrawn from the study at the discretion of the study investigator. Each participant, with the help of a guardian, will insert a non-blinded sensor according to the Dexcom G6 user guide, connect the Dexcom to a compatible phone, and activate the share functions with the clinic. If the guardian is not able to set-up the Dexcom at home, the patient and guardian will be asked to come for Visit 2B within 5 days to have the non-blinded Dexcom set-up in clinic and assure that inserting the CGM is a skill that could be done independently. If the guardian or participant cannot demonstrate that they can set-up the CGM system independently, the participant will be withdrawn from the study.

Between Visit 2T and Visit 3, clinic research staff will actively monitor the participants' blood glucose levels remotely through an Apple iPad. Currently available commercial Dexcom software is able to monitor up to 10 devices on a single iPad, and we plan to have two iPads

throughout the study period. Active remote monitoring of CGM data will occur during 7 days per week between 8:00 AM and 8:00 PM.

The goal of the secure text messaging is to provide supervision and feedback to the adolescents that is supportive and collaborative, with the ultimate goals of increasing self-efficacy and improving diabetic self-management skills. The intention is not to make the texting platform cumbersome and to allow the participants freedom in making lifestyle choices that will not interfere with their diabetes control. Only reactive texts and coaching texts will be sent during the school hours.

Participants will still be able to use normal clinic communication methods through the electronic patient portal and diabetes telephone emergency line as usual. Participants will be free to optimize their treatment independently as previously educated about trend management. We will provide a letter for school indicating that the participants are a part of a study and they have to carry their cell phones with them and respond to text messaging from us.

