Collaborative Parent Involvement Scale		X		X	X

[figure not shown]

Figure 1. Timeline for study. Study visits are denoted by arrows. A timescale in months is below the timeline; there is not a specified interval between Visits 1 & 2.

Participant withdrawal criteria

The following study withdrawal criteria will apply:

1. Participants can terminate involvement in the study at any time point without any repercussions.
2. If data on the CGM is available < 60% of the time worn, patient may be withdrawn at the discretion of the research investigator.
3. If pregnancy occurs during study period.
4. Allergic reaction to adhesive surface of CGM sensor

Primary endpoint

The primary outcome is change in Hemoglobin A1c (HbA1c) between the baseline visit (Visit 2) and three-month follow-up visit (Visit 3) after active remote monitoring and secure text messaging.

A 5% significance level will be used to declare statistical significance for the primary outcome comparison.

Exploratory endpoints

- Change in Peds PHQ-9A, PED-QOL4A, SEDM, and Collaborative Parent Involvement Scale scores.
- Time taken for a text to be read by participant and guardian.
- Time spent by medical provider per participant per day.
- The difference in A1c between clinical remote monitoring HbA1c (Visit 3) and self-monitoring utilizing CGM (Visit 4)
- The difference in A1c from baseline (Visit 2) and after the two phases of the study intervention (Visit 4).
- The following outcomes will be compared between baseline, three months and six months using repeated measures ANOVA as follows:
 - Time spent in the target glucose range from 70–180 mg/dL
 - Time spent below target glucose 70 mg/dL

- Time spent above target glucose 180 mg/dL
- Average of time the participants wore the CGM

Statistical Plan

Paired sample t-tests will be used to assess continuous variable differences between two time points. Generalized linear models will be run to identify items in medical and social histories that could predict hemoglobin A1c, the primary outcome. Point estimates will be reported with 95% CIs.

As this is a pilot exploratory study, we will implement per-protocol analysis and not an intention-to-treat analysis. Only patients who have completed the three phases of the study will be included for analysis.

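### CGM wear is compared over time against the same run-in measurement that helps decide who continues, so part of any change from baseline may be an artefact of selection

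*Combined protocol and SAP*

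**What the plan says.** The list under Exploratory endpoints introduces four CGM outcomes with "The following outcomes will be compared between baseline, three months and six months using repeated measures ANOVA as follows". The last of them is "Average of time the participants wore the CGM". No unit, window or further definition is given there.

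The baseline value comes from the first phase, described in Overview of methodology: a "blinded Dexcom G6 will be used to obtain baseline values including time in range, percent highs, and percent lows, and percent CGM use". The same section gives that phase a second purpose: "We will use this phase as a run-in period to reduce the chance of noncompliance with the study". It then sets the threshold: "Participants who wore the device at least 60% of the time will then proceed to the second phase of the study". Below 60%, "the participant may be withdrawn from the study at the discretion of the study investigator"; the Visit 2B or 2T section repeats this.

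The measurement conditions differ between periods. At Visit 2, "A blinded CGM will be placed on the participant with the goal to obtain baseline data for 10 days". During that time "participants and clinical staff will be notified if there is signal loss from the blinded CGM", and the manufacturer troubleshoots technical problems. From Visit 2T or 2B the participant inserts the sensors with a guardian's help. Visits 3 and 4 each follow 11 to 12 weeks later, and Data management calls for 90-day aggregate CGM reports.

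The Statistical Plan restricts the analysis to participants who complete all three phases.

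**The concern.** One measurement has two jobs. Run-in wear helps to choose who continues, and it is also the first point of the comparison over time. Wear varies within a person. Someone who passes a threshold partly because of a good ten days will, on average, record lower wear later with no change in behaviour. Because only completers are analysed, anyone withdrawn for low run-in wear is missing from every time point, so the baseline mean of the analysed group is raised relative to its own typical wear.

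Baseline is also not the same quantity as the later values. It reflects about ten days that begin with a sensor placed on the participant at Visit 2. The later values reflect repeated self-insertion over nearly three months.

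Wear is a direct measure of whether these adolescents will use the system, in a trial whose title begins with feasibility. The three-point test could report declining adherence that is partly an artefact, or mask a real gain in wear while staff are monitoring. Nothing in the plan adjusts for the selection or warns about interpretation.

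**Working it through.** **The plan's own figures.** The plan gives no expected mean, SD or correlation for wear. Its only sample-size figure is for HbA1c. Taking 1.5 as the SD of the change, (1.5 × (1.960 + 0.842) / 1)² = 17.66, rounded up to the stated 18. This reproduces, but it has no bearing on wear.

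**Model.** Observed wear in each period is a person's true wear plus independent within-person variation, with true wear unchanged. Let SD = √(between² + within²), r = between²/SD² and a = (60 − mean)/SD. Write φ and Φ for the standard normal density and distribution function.

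- Strict cut: expected fall = (1 − r) × SD × φ(a) / (1 − Φ(a)).
- Half of those below 60% kept: with F the strict fall and p the proportion below 60%, expected fall = ½ × F × (1 − p) / (1 − p/2). Over everyone the changes average zero, so those kept from below 60% cancel half of the effect.
- Nobody withdrawn: 0.

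**Assumed scenarios.** Values are in percentage points. They were simulated with 1,000,000 participants each and wear limited to 0–100%; the formulas agree to within 0.1.

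| Mean / between SD / within SD | SD | r | Below 60% | Strict | Half kept | None withdrawn |
|---|---|---|---|---|---|---|
| 75 / 12 / 8 | 14.4 | 0.69 | 15% | 1.2 | 0.6 | 0 |
| 70 / 15 / 10 | 18.0 | 0.69 | 29% | 2.7 | 1.1 | 0 |
| 70 / 15 / 15 | 21.2 | 0.50 | 32% | 5.5 | 2.2 | 0 |
| 60 / 20 / 15 | 25.0 | 0.64 | 50% | 7.1 | 2.4 | 0 |

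Example, second row: a = (60 − 70)/18.03 = −0.555, and φ(a)/(1 − Φ(a)) = 0.481. The strict fall is (1 − 0.69) × 18.03 × 0.481 ≈ 2.7. With half kept it is ½ × 2.7 × 0.71 / 0.855 ≈ 1.1.

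**Wider range.** Over means of 65–85%, SDs of 15–25 and r from 0.3 to 0.9, the strict-cut formula gives falls of 0.2 to 11.8 points. At mean 75, SD 20 and r = 0.5 it gives 0.5 × 20 × 0.389 = 3.9.

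**Selection on later wear as well.** If the run-in cut is strict and half of those below 60% in phase 2 also drop out of the analysed set, the fall from baseline to phase 2 is about 0.6 to 4 points in the four scenarios. If selection is equally strict at both times, it nets to about zero.

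**Phase 2 against phase 3.** With run-in selection only, the artefact in this contrast is 0.0 points in all four scenarios, because neither window is the selecting measurement. If half of those with low phase 2 wear are also lost, a fall of about 0.4 to 2 points appears.

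**Window and placement.** The documents contain nothing from which to size this difference.

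**The case against.** The strongest reply is that the selection is softer than a strict cut. Participants at 60% or more proceed, but those below may be withdrawn only at the investigator's discretion. This stands: the strict figures are the upper case for each scenario, and the artefact vanishes if nobody is withdrawn.

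Second, other forces push the opposite way. The completers-only set and the general <60% rule under Participant withdrawal criteria, which is not confined to the run-in, can remove people with low later wear. In phase 2 staff text after four hours without data and follow up an unanswered text with a call, which may raise wear. This also stands. A reader might infer that the trial will show a spurious decline in wear. The documents do not support that: they show a downward component if the cut is applied, not the sign of the net change. Nor do they say who places the Visit 2 sensor, so calling baseline staff-placed is an inference.

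Third, a reader might take phase 2 against phase 3 as a clean estimate of the effect of monitoring. It is not. Phase 3 always follows phase 2 in a single arm, so the contrast is confounded with time, and it can carry its own selection artefact.

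Fourth, wear is one exploratory outcome in an uncontrolled pilot of 25. With 20 completers and a strict cut, the 95% half-width for the change from baseline is about 5 to 8.5 points across the four scenarios, wider than the artefact in each. That lowers the severity. It does not make baseline a suitable comparator.

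**Conclusion.** The point holds as a component of bias, not as a prediction of the result. Run-in wear is both a selection variable and the first point of the wear comparison among completers. Where the cut is applied and wear varies within a person, that contributes a fall unrelated to behaviour: about 1 to 7 points if strict, about 0.6 to 2.4 if half of those below 60% are kept, and none if nobody is withdrawn. All of these sizes rest on assumed means, SDs and correlations. Opposing influences leave the net direction undetermined. The mismatch in window and sensor placement weakens comparability further by an amount that cannot be sized. The endpoint is exploratory and the HbA1c primary analysis is untouched, so this is a low-severity point with an inexpensive remedy.

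**What to change.** 1. Remove baseline from the wear ANOVA.
2. Report wear in phase 2 (Visit 2T/2B to Visit 3) against phase 3 (Visit 3 to Visit 4) as a paired difference with a 95% CI. Include all who entered phase 2 and have wear data for both windows, including anyone withdrawn for low wear where data exist.
3. Bound the windows by visit dates. Visits 11 to 12 weeks apart (± 5 days) are 72 to 89 days apart, so a 90-day report ending at Visit 4 would reach 1 to 18 days back into phase 2.
4. State that this contrast is uncontrolled and confounded with time.
5. Report run-in wear descriptively for everyone fitted with the blinded sensor, with the number not continued because of wear below 60%.

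The cost is a few sentences in Exploratory endpoints and the Statistical Plan. Paired comparisons with 95% CIs are already planned, and week-by-week CGM data are already to be collected, so no new visits, data or participants are needed. The one loss is a before-after claim on wear, which the run-in cannot properly support.

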We will discuss that CGMs will continue to be made available to participants and guardians for diabetes care. Participants and guardians will still be able to communicate with our clinic through previously available means, mainly through the electronic participant portal and/or calling the urgent line, and they could ask the clinic staff to review past CGM readings to give clinical advice.

Second Follow-up, Visit 4/EOSV

This visit will be scheduled 11-12 weeks (+/- 5 days) after Visit 3. Adverse events, insulin doses and concomitant medications will be reviewed by study staff. Height and weight will be measured, and a physical exam will be performed. A capillary blood sample will be obtained for HbA1c. Participants will complete the PHQ-9A and PEDS-QoL4 surveys, Collaborative Parent Involvement Scale, and SEDM.

If due to participant or family scheduling conflicts, the participant is unable to complete a clinic visit for Visit 4, then they can participate in a telemedicine visit. Participants will be requested to measure height and weight at home. A physical exam will be performed as fully able within the telemedicine platform. HbA1c will be obtained with other standard of care labs. CGM report analysis will not be affected by the telemedicine visit. Surveys for PHQ-9A, PEDS-QoL4, Collaborative Parent Involvement Scale, and SEDM will be sent via MyChart to the participant's parent to be completed by the participant. Parents will send images of the completed surveys to the research team via MyChart.

This is the final study visit.

Evaluations

Medical History

- Age
- Gender
- Race/ethnicity
- Date of diagnosis of type 1 diabetes
- Hospitalizations and emergency department visits, particularly for diabetic ketoacidosis or hyperglycemia/ketosis/vomiting, or for severe hypoglycemia
- Surgeries
- Growth records for both height and weight
- Current doses of insulin
- Meal plan
- Other chronic medical conditions, particularly hypothyroidism or celiac disease
- Concomitant medications

Social history

- Family structure—one or two parent household, parents married or divorced, custody arrangements if divorced, genders and ages of siblings

- School details: name, grade, extracurricular activities, sports, schedule, school nurse information, and information about student insulin dosing during school hours if it is done through school nurse or independently by student.

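### The primary Visit 2 to Visit 3 HbA1c analysis excludes anyone who leaves in the later, exploratory phase 3, which discards observed primary data and may bias the result

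*Combined protocol and SAP*

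**What the plan says.** All references are to the combined protocol and SAP.

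- **Primary endpoint:** "The primary outcome is change in Hemoglobin A1c (HbA1c) between the baseline visit (Visit 2) and three-month follow-up visit (Visit 3", the visit that closes the remote-monitoring phase. It is tested at the 5% level.
- **Statistical Plan:** "we will implement per-protocol analysis and not an intention-to-treat analysis", with pilot status as the reason. The next sentence is "Only patients who have completed the three phases of the study will be included for analysis". It makes no exception for the primary endpoint.
- **Second Follow-up, Visit 4/EOSV:** "This visit will be scheduled 11-12 weeks (+/- 5 days) after Visit 3". Phase 3 therefore lies wholly after the primary measurement.
- **Overview of methodology**, on phase 3: "This study phase will be exploratory to assess whether any improvement in diabetes control" persists once monitoring is withdrawn.
- **CGM wear.** Overview of methodology: "Participants who wore the device at least 60% of the time will then proceed to the second phase of the study". That section and the Visit 2B/2T section add that participants below 60% wear may be withdrawn at the investigator's discretion. Participant withdrawal criteria, item 2: "If data on the CGM is available < 60% of the time worn, patient may be withdrawn at the discretion of the research investigator".

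The documents contain no all-available-data analysis, missing-data method or assumed dropout rate.

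**The concern.** Entry to the primary analysis depends on something that happens after the primary outcome has been measured. A three-month question, even one answered per protocol, does not require completion of the following three months.

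Two kinds of loss need to be kept apart. A participant who leaves in phase 3 has both primary values, and the plan deletes them. A participant who leaves in phase 2 will usually have no Visit 3 value. That is a missing-data problem, and the plan removes the person without comment.

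If leaving is related to response, the completer mean does not estimate the effect in those who started the intervention. There is no control arm in which the same selection would show. The probable direction is toward benefit: the Background section ties HbA1c reduction to regular CGM use, and participants who disengage are likely to be the less regular users.

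**Working it through.** **Inputs from the documents.** Enrolment 25 (Study design). SD 1.5%, difference 1%, alpha 0.05, power 80%, required n = 18 (sample-size paragraph following the Statistical Plan). Test: paired t-test (Statistical Plan).

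**Assumptions.** 1.5% is taken as the SD of the change. If it is the SD of HbA1c itself, a within-patient correlation of 0.5 gives the same SD of change. The test is taken as two-sided, which is not stated but reproduces the plan's n.

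**1. The plan's own figure.** n = (1.5 × (1.960 + 0.842) / 1)² = 17.66, rounded up to 18. It reproduces by the normal approximation. The exact paired t-test needs 20: its power is 76.0% at 18, 80.7% at 20 and 89.2% at 25.

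**2. Precision lost by deleting observed pairs.** This needs no assumption about bias. Assume 22 have a Visit 3 HbA1c and 4 of them leave in phase 3. The 95% CI half-width is t(0.975, n-1) × 1.5/√n.

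| n analysed | Half-width (points) | t-test power for a 1% change |
|---|---|---|
| 22 | 2.080 × 1.5/√22 = 0.67 | 84.6% |
| 18 | 2.110 × 1.5/√18 = 0.75 | 76.0% |

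**3. Possible bias.** Let 18 completers have mean change -1.0, and let k other participants who started phase 2 have mean change c. The mean over all starters is (18 × (-1.0) + k × c)/(18 + k). The completer estimate relative to it is 1.0 divided by the absolute value of that mean. The range k = 2 to 7 covers 20 to 25 starters.

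| c | k = 2: all-starter mean, error | k = 7: all-starter mean, error |
|---|---|---|
| 0 | -18/20 = -0.90, 11% too large | -18/25 = -0.72, 39% too large |
| -0.5 | -19/20 = -0.95, 5% too large | -21.5/25 = -0.86, 16% too large |
| -1.0 | -1.00, none | -1.00, none |
| -1.5 | -21/20 = -1.05, 5% too small | -28.5/25 = -1.14, 12% too small |

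**4. Effect on the test.** A simulation used 25 starters, 18 retained, SD 1.5, true change zero and 100,000 runs. The correlation between retention and HbA1c improvement is an assumption.

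| Correlation | Shift in mean (points) | False-positive rate for benefit (nominal 2.5%) |
|---|---|---|
| -0.3 | +0.21 | 0.6% |
| 0 | 0.00 | 2.5% |
| 0.3 | -0.20 | 8.3% |
| 0.5 | -0.34 | 16.8% |

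With 20 retained, correlations of 0.3 and 0.5 give shifts of -0.15 and -0.25 and rates of 6.5% and 12.1%.

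**The case against.** The plan declares a per-protocol pilot analysis in advance and enrols 25 against a required 18, so some loss can be absorbed. Nothing in the documents gives a dropout rate or links dropout to response. All of this is true, and it limits what can be said about size and direction. It does not justify deleting observed pairs: the study states an efficacy hypothesis, tests it at 5% and is powered for it, and declaring a selection rule does not remove its effect.

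A reader might infer more than the text supports:

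- **That the result is biased toward benefit.** This is probable, not shown. There is no bias if nobody leaves or if leaving is unrelated to response, and the sign reverses if leavers improve more.
- **That the overstatement is 39%.** That is the extreme of the table. It needs all 25 enrolled to start phase 2 and 7 leavers with exactly zero change. Losses in the blinded run-in precede the intervention and mainly affect generalisability.
- **That all losses condition on post-outcome events.** Only phase 3 losses do.
- **That feasibility cannot be assessed because retention is 100% by construction.** The completer rule fixes the analysis set. Withdrawals can still be counted against the 25 enrolled.
- **That the 60% rules contradict each other and let investigators remove non-adherent participants at any time.** The Overview sentences cover complementary groups: those at or above 60% proceed, and those below may be withdrawn. Withdrawal criterion 2 does differ, with data available as a share of time worn and no stated phase. Read literally, however, a participant who simply takes the sensor off does not trigger it. The sound point is narrower: the passages differ in denominator and phase.

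**Conclusion.** The concern holds for the completer restriction and should be fixed before analysis. As written, the plan removes participants with both primary HbA1c values because of events in a later exploratory phase, and nothing elsewhere in the documents repairs this.

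The loss of data follows from the text whenever a participant with a Visit 3 value leaves in phase 3. Its cost in precision depends on how many do so; the 22-to-18 example is an assumption. Bias is possible and probably favours benefit, but its size and even its sign rest on attrition and response figures that the documents do not give. The tables above are illustrations under stated assumptions, not estimates for this trial.

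**What to change.** In the Statistical Plan:

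1. Define the primary analysis set as all participants who start unblinded CGM with remote monitoring at Visit 2T/2B. Run the planned paired t-test on everyone in that set who has Visit 2 and Visit 3 HbA1c, regardless of phase 3 completion or CGM wear.
2. State that low CGM use does not remove an observed HbA1c from analysis.
3. Keep the three-phase completer set for the Visit 4 comparisons and as a sensitivity analysis of the primary endpoint.
4. Add a sensitivity analysis for missing Visit 3 values, because step 1 recovers phase 3 leavers but not those lost in phase 2 without a measurement. A mixed model is one option. It assumes missing at random, so it does not by itself cure response-related dropout.
5. Report withdrawals by phase and reason.

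Separately, the 60% statements in Overview of methodology, the Visit 2B/2T section and withdrawal criterion 2 differ in denominator and phase and must be reconciled.

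The cost is SAP wording and a little more analysis, with no added patients or visits. The estimate may be slightly less favourable.
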